9.7.5 Planned Analysis for the Exploratory Objective

9.7.5.1 Identification of subgroups among patients with similar profile with clustering models

The identification of subgroups among patients with similar profile will be descriptive and exploratory in nature with the variables listed in the table XX. The analysis will be run following the clustering models like K-Means, Random-Forest or Ascending hierarchical clustering. Data visualization will be also presented.

9.7.6 Sensitivity analyses

We will perform the following sensitivity analyses:

1. Analyses on the evaluation of the incidence rate and comparison of the events of interest (stroke, major bleeding, and death) will be performed from the inclusion date for all incident AF patients (i.e. the inclusion date will be the index date for all incident patients, whether or not patients received OAC therapy within 30 days of the inclusion date).
2. Analyses including the 2020 data (given the uncertainty of the impact of the Covid 19 health crisis on the management of NVAF incident patients) will be conducted on:
 - Description of the follow-up of the study population (Table A1);
 - Sociodemographic characteristics (Tables A4 and A7), medical history and comorbidities (Table A5 and A8); concomitant treatments (Tables A6 and A9);
 - Estimation and comparisons of the incidence of interest-events in AF exposed and unexposed to OAC (primary objective - Table A2, secondary objective - Table A10);
 - Estimation of the annual incidence rate and the prevalence of AF patients (Tables A12 and A13 respectively).
3. Analyses on AF patients without the second inclusion criteria (new OAC users identified by the algorithm of *Billionnet et al.* not included) will be performed for the estimation of the annual standardized incidence and prevalence (Tables A12 and A13 respectively).
4. Analyses will be considered to test the impact of different grace periods (duration of 30 days and 90 days) in the calculation of treatment sequences for the following objectives:
 - Estimation and comparisons of the incidence of interest-events in AF exposed and unexposed to OAC (primary objective - Table A2, secondary objectives - Table A10)
5. If more than 10% of each event of interest occur during the 60 days grace period, analyses will be performed considering this event of interest in an unexposed period for the following objectives:

- Estimation and comparisons of the incidence of interest-events in AF exposed and unexposed to OAC (primary objective - Table A2, secondary objectives - Table A10)

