3.5.2. Exposure

Exposure to an OAC is defined by an initiation of VKA, apixaban, dabigatran or rivaroxaban. AF patients unexposed to OAC are defined by a first diagnosis of AF without OAC treatment.

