3.7.5 Sensitivity analyses

We will perform following sensitivity analyses:

- All analyses will be conducted including the 2020 data, given the uncertainty of the impact of the Covid 19 health crisis on the management of AF patients
- AF patients without the second inclusion criteria, OAC new users identified by algorithm used in NACORA study to estimate the standardized incidence rate and prevalence.

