9.2.3 Patient Selection

9.2.3.1 Inclusion Criteria

Patients will be included in the study if they meet the following inclusion criteria:

- Age ≥18 years old at index date

AND

(

- Patients with at least one hospital stay with a principal (PD), related (RD) or associated (AD) diagnosis (in PMSI-MSO) of code I48 (Atrial fibrillation of the International Classification of Disease 10th version, ICD-10) or with an active Long-Term Disease (LTD) with ICD-10 code I48 during the study (historical or inclusion) period

AND/OR

- Patients who are new users of OACs for the AF treatment with or without AF diagnosis (PMSI-MSO or LTD), identifying with a validated and published algorithm with a high specificity (c-index 0,93), using a predictive model developed by Billonnet et al. (16).

)

Description of the algorithm:

The algorithm for identifying patients exposed to OAC indicated for AF will be based on the patients who receive at least one reimbursement of an OAC (VKA, apixaban, rivaroxaban or dabigatran) during the inclusion period, without use of any OAC in the 24 months prior to the first reimbursement date.

Patients reported with at least one orthopedic procedure (osteoarticular or muscular) of the lower limb (including hip/knee replacement) as corresponding to the indication of primary prevention of venous thromboembolic events, during a 6-week period before the first date of OAC delivery will be excluded.

Then, three groups of patients will be identified:

- Confirmed AF are defined as patients with at least one hospital stay with a PD, RD or AD of code I48 or with an active LTD with ICD-10 code I48 or with an electrical cardioversion procedure or radiofrequency ablation before the first date of OAC delivery during the historical period;
- Confirmed DVT/PE are defined as patients hospitalized with a diagnosis of PE (code I26 in any position) or DVT (codes I80 except I80.0, I81, I82 in any position) or with a doppler ultrasound examinations, CT venography, MR venography or pulmonary scintigraphy during a 6-week period before the first date of OAC delivery;
- Unclassified patients in other cases.

Patients with both confirmed AF and DVT/PE will be excluded.

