Then, a logistic model included 14 independent covariables will be applied on unclassified patients to identify AF outpatients. The model will include following covariables: age, gender, use of treatments as use of beta-blockers, antiarrhythmics, antihypertensive drug, holter/echocardiography procedures, cardiologist prescriber, D-dimer blood test reimbursement and presence of hospitalization for arterial thromboembolic event.

Finally, for each unclassified patient, those with a predicted probability above the cut-off value providing specificity of 95% (sensitivity: 63%), will be assumed to be AF outpatients.

9.2.3.2 *Exclusion Criteria*

Patients will be excluded from the study if they meet any exclusion criteria:

- Patients with at least one hospital stay with an ICD-10 code in PD, RD or AD for associated valve disease, ICD-10 codes I05 to I09, I34 and I39, or valve surgery;
- Standard SNDS exclusion criteria (e.g. unicity of identifier not guaranteed, twins, aberrant demographic data, beneficiaries from Mayotte overseas French territory).

[figure not shown]

Figure 2. AF study population according to inclusion and non-inclusion criteria

9.2.3.3 *Populations*

Two populations of AF patients will be considered for analyses according to study objectives:

9.2.3.3.1 *Prevalent AF population*

Prevalent AF patients will be defined as patients diagnosed with AF during the historical period.

Prevalent AF population will be considered for the following analysis:

- To estimate the annual prevalence of patients with non-valvular AF, exposed and unexposed to OAC (objective 4).

9.2.3.3.2 *Incident AF population*

Incident AF patients will be defined as patients newly diagnosed with AF (i.e. no AF diagnostic during the historical period) from January 1st, 2016 to December 31st, 2019 (inclusion period), and to December 31st (2020 for sensitivity analyses).

For incident AF population, two datasets of incident AF patients will be considered for the following analyses:

- For longitudinal analyses: objectives 1, 2, 3 and 7 (cf. 8. Objectives)

Inclusion of patients with:

- An AF newly diagnosed during inclusion period

AND

- No reported events of interest (stroke, major bleeding, and death) within 30 days before index date (i.e. for patients for whom the date of inclusion is not the date of the first dispensation of OA) (cf. 9.2.3.1. Inclusion Criteria)

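### The analysis that drops algorithm-identified patients should extend to the exposed-versus-unexposed event rates and hazard ratios, which are open to selection bias by route of AF identification

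*SAP*

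**What the plan says.** SAP 9.2.3.1 gives two ways in. The first is diagnostic: "Patients with at least one hospital stay with a principal (PD), related (RD) or associated (AD) diagnosis (in PMSI-MSO) of code I48"), or an active LTD with that code. The second is drug-based: "Patients who are new users of OACs for the AF treatment with or without AF diagnosis (PMSI-MSO or LTD"). The algorithm behind the second route "will be based on the patients who receive at least one reimbursement of an OAC (VKA, apixaban, rivaroxaban or dabigatran"). New users who are neither confirmed AF nor confirmed venous thromboembolism are scored by a logistic model, and "those with a predicted probability above the cut-off value providing specificity of 95% (sensitivity: 63%), will be assumed to be AF outpatients".

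Protocol 3.5.2 defines the comparison group: "AF patients unexposed to OAC are defined by a first diagnosis of AF without OAC treatment". SAP 9.3.1.1 adds that LTD registration is not mandatory and may be missing, for example when another chronic disease already covers the expenses or the treatment is cheap.

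Both documents plan an analysis without algorithm entrants. Protocol 3.7.5 describes it as "AF patients without the second inclusion criteria, OAC new users identified by algorithm used in NACORA study to estimate the standardized incidence rate and prevalence". Item 3 of SAP 9.7.6 says the analyses "will be performed for the estimation of the annual standardized incidence and prevalence (Tables A12 and A13 respectively"). SAP Table XXI lists it under the incidence and prevalence objective only.

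**The concern.** The two groups are not found in the same way. The OAC-free time that precedes any treatment comes only from patients with an I48 hospital stay or an LTD. Exposed time comes from such patients and also from outpatients who have neither and are recognised because they filled an OAC prescription. If event rates differ between these two kinds of patient, exposed and unexposed rates will differ even where OAC does nothing.

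This touches the centre of the study. Its stated rationale (SAP 7.2) is the lack of data on unexposed patients. Rates in exposed and unexposed patients are the primary objective, and comparing them is a secondary one. Protocol 2.4 foresees use of the results in submissions to health authorities. The sponsor saw a reason to test dependence on the algorithm, but not for these results.

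**Working it through.** The plan states no figure to reproduce on this point. The check has two parts.

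**1. Does anything else in the plan deal with the route of entry?**

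- *Primary rates (SAP 9.7.3.1, Tables A2 and A3).* Unexposed rates are standardised to the exposed population on age group only. Table A2 is repeated in the subpopulations and risk strata, but not by route.
- *Cox models (SAP 9.7.4.2, Table XV, footnotes to Tables A10 and A11).* No covariate records route of identification or hospitalisation at entry. Table XV includes frailty, the Charlson index, CHA2DS2-VASc and HAS-BLED; the footnotes give a shorter list without them. Several covariates rest on hospital codes alone (malnutrition, morbid obesity, history of major bleeding in Table VI). Others rest largely on hospital or LTD codes. Patients who enter through a hospital stay therefore have more opportunity to have them recorded. Concomitant treatments are dispensing-based and do not have this problem.
- *Other sensitivity analyses of Tables A2 and A10 (SAP 9.7.6).* These vary the start date, the 2020 data, the grace period and the handling of grace-period events. None varies the route.
- *Limitations (SAP 9.9, Protocol 3.8).* The issue is not mentioned.

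**2. How large could a pure route effect be?**

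The documents give neither the share of algorithm-only entrants nor any event rate by route. All inputs below are assumptions, with OAC set to have no effect.

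- s = share of exposed person-time from algorithm-only entrants, 20-50%.
- r = their event rate divided by that of hospital/LTD entrants, 0.4-0.7.
- u = share of unexposed person-time from algorithm-only entrants, 0 or 10%. It is not necessarily zero, because SAP Table VII counts time after stopping OAC as unexposed.

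Spurious exposed/unexposed rate ratio = [(1 − s) + s·r] / [(1 − u) + u·r]

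| s | r | Numerator | Ratio, u = 0 | Denominator, u = 10% | Ratio, u = 10% |
|---|---|---|---|---|---|
| 20% | 0.7 | 0.80 + 0.14 = 0.94 | 0.94 | 0.90 + 0.07 = 0.97 | 0.97 |
| 35% | 0.5 | 0.65 + 0.175 = 0.825 | 0.83 | 0.90 + 0.05 = 0.95 | 0.87 |
| 50% | 0.4 | 0.50 + 0.20 = 0.70 | 0.70 | 0.90 + 0.04 = 0.94 | 0.74 |

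The ratio is 1.00 if r = 1 (no rate difference by route) or if u = s (same mix in both groups). With s above u, it exceeds 1 if r is above 1. Restricting to hospital/LTD entrants sets s = u = 0, so the ratio is 1.00 whatever r is.

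**The case against.** The strongest case against is that no bias has been shown. A reader might infer from the entry rules that the results *are* confounded and that OAC will look falsely protective. The documents do not support that. They give no rates by route, and algorithm entrants are not uniformly low-risk: the model includes a recent hospitalisation for arterial thromboembolism (SAP Table III). Hospital entrants qualify on I48 in any diagnostic position, which can include incidental AF. This objection stands.

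A reader might also infer that untreated outpatients are invisible. They are not: an LTD is requested by the general practitioner, so some enter that way, although capture is incomplete. Time off treatment among algorithm entrants dilutes the asymmetry further, as the right-hand column of the table shows. Both points stand as qualifications.

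The Cox models adjust for many markers of severity, so it would be too strong to say that the planned analyses cannot separate route from treatment at all. They do so in part. The illustration above ignores that adjustment and the age standardisation.

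Finally, the primary analysis is descriptive, and DOAC-versus-VKA contrasts do not have this asymmetry because both groups can use both routes. That lowers the severity. It does not remove the point: standardising unexposed rates to the exposed population invites a comparison, and objective 3 makes one.

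**Conclusion.** The asymmetry of entry is a matter of record, and no planned analysis of Tables A2, A3, A10 or A11 tests it. Those exposed-versus-unexposed results are open to selection bias by route of AF identification. Age standardisation does not address it, and the Cox covariates address it only in part.

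Size and direction are unknown. The illustrative ranges (about 0.70-0.94, or 0.74-0.97 with 10% of unexposed time from algorithm entrants who stopped) rest wholly on assumed shares and rates, before any adjustment. They show only that a route effect could be large enough to matter.

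A reader might conclude that the restricted cohort should replace the full one for these comparisons. That does not follow: restriction changes the target population, and it leaves confounding by indication in place. This is a change that should be made. It is not a fault that invalidates the plan.

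**What to change.** 1. Extend item 3 of SAP 9.7.6 to Tables A2, A3, A10 and A11, restricted to patients with an I48 hospital stay or LTD on or before the index date. State that date rule explicitly. The present wording only removes algorithm entrants and does not say how to treat a patient whose first AF code comes after an algorithm-based entry.
2. Report the algorithm-only share of person-time separately for exposed and unexposed time.
3. Interpret the full-cohort exposed-versus-unexposed results alongside the restricted ones, and add the issue to SAP 9.9.
4. Optionally, add route of identification as a covariate in the full-cohort Cox models. This is a supplement only: its algorithm-only level contains no never-treated patients, and its unexposed time comes solely from patients who stopped.
5. Keep DOAC-versus-VKA contrasts on the full cohort.

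The cost is SAP wording, possibly a small re-derivation of the restricted dataset for the date rule, and reruns of four tables on data already extracted. The price in inference is fewer exposed patients in the restricted analysis and a result that applies only to AF identified by hospital stay or LTD.

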9.8 Quality Control

At the study level, all aspects of the study from protocol development to the reporting of the results are conducted within the work-frame of IQVIA Quality Management System and in accordance to the following policies and procedures:

- RWI_OP_RWW0009 "Retrospective Database Studies"
- RWI_OP_BIOS0003 "Statistical Analysis Plan for retrospective database studies"
- RWI_WI_EPI0005 "Real-World Protocol development"
- RWI_OP_PM0020 "Real World Records Management"

According to the policies and procedures above, a Quality Control plan for the study will be developed and executed, which will include quality control on study methodology, statistical analysis plan, programming, data management and analysis, study results, conclusions and study report. Furthermore:

- The study Quality Control plan will establish ownership for the execution of the individual Quality Control steps. The principle of the independence of Quality Control applies
- The Principal-in-Charge of the study will ensure that individuals responsible for the execution of specific Quality Control steps will have knowledge, capability and experience which are adequate for the task.
- The result of the execution of the individual steps of the Quality Control plan will be documented, and include the required corrective actions, if any.
- The execution of any required corrective action will be documented.
- The executed Quality Control plan will be subjected to a final review and approval for sufficiency and completeness from the Principal-in-Charge of the study

Also, the Principal-in-Charge of the study will verify training compliance of IQVIA employees contributing to the study, as per IQVIA procedure RWI_WI_PM0035 "Real-World Project Specific Training and Staff Transition.

9.9 Limitations of the study

Limitations of this study include those inherent to the use of retrospective administrative claims data and limitations associated with missing data. Several limits related to the use of SNDS data have been identified in this study, no biological and clinical information were available for this study. The drug intake of patients is not measurable. Health insurance scheme: the dates of death and information on long term disease (LTD) for the self-employed and agricultural schemes (MSA/RSI) as well as for SLMs (government employees and student schemes) are partially available in the DCIR.

10 Protection of Human Subjects

The ethics approval process is complex, requiring approval from several committees although it has been simplified in February 2020.

The Health Data Hub (HDH), responsible for facilitating access to healthcare data. HDH checks the completeness of the ethics application submitted and transfers it to the two following committees:

- *Comité Éthique et Scientifique pour les Recherches, les Études et les Évaluations dans le domaine de la santé* (CESREES);
- *Commission Nationale de l'Informatique et des Libertés* (CNIL).

CESREES is the expert committee for research, studies and evaluations in the field of health. It advises on the methodology adopted on the need for the use of personal data, their relevance, the scientific quality and the public interest of the project. It is composed of 21 members from the public and private sectors, representing various skill sets: epidemiology, sociology, philosophy, ethics, law, health economics, medicine, pharmacy, health democracy, hospital administration, industry (digital and health products), innovation and participatory open science.

The CNIL is the national commission for information technology and freedom, who regulates personal data, assisting professionals in their compliance and helps individuals to control their personal data and exercise their rights.

11 Management and Reporting of Adverse Events/ Adverse Reactions

Pursuant to the European Medicines Agency requirements for reporting of adverse events for secondary data (Good Pharmacovigilance Practices module VI, VI.C.1.2.1.2), adverse event reporting will not be conducted as part of this study given the study objectives will be met through the use of secondary data.

12 Plans for Disseminating and Communicating Study Results

Appendix 1 - Design for analyses performed on incident AF patients (objectives 1, 2, 3 and 7)

Principal analysis

1

Sensitivity analysis

2

Appendix 2 Calculation of Claims-based Frailty Index (CFI)

Claims-based frailty index (CFI) estimates a deficit-accumulation frailty index from a clinical assessment using International Classification of Diseases (ICD) diagnosis codes, Current Procedural Terminology (CPT) codes, and Healthcare Common Procedure Coding System (HCPCS) codes in the prior 2 years in administrative claims data.

Interpretation: Analogous to a deficit-accumulation frailty index, the CFI gives a score ranging from 0 to 1 with a submaximal limit around 0.6-0.7. In the analysis, it can be used as a continuous variable or as a categorical variable with the following suggested cut-points: non-frail <0.10, prefrail 0.10-0.19, mildly frail 0.20-0.29, moderately frail 0.30-0.39, and severely frail ≥ 0.40 . The latter three categories could be combined as frail (≥ 0.20).

Validation: Performance of CFI against clinical assessments of frailty and functional status:

- Frailty phenotype: C-statistic 0.78
- Deficit-accumulation frailty index: Spearman correlation 0.59
- ADL dependency: C-statistic 0.81
- ≥ 2 ADL dependency (severe disability): C-statistic 0.84

Program Download: <https://dataverse.harvard.edu/dataverse/cfi/>

Appendix 3 Shell Tables and Examples of Figures

Table A1. Description of the follow-up of the AF incident population	97
Table A2. Incidence rate for stroke, major bleeding and death in AF incidents patients between 2016 and 2019 in France – <POPULATION>	98
Table A3. Incidence rate for ischemic and hemorrhagic stroke in AF incidents patients between 2016 and 2019 in France	99
Table A4. Description of sociodemographic characteristics in AF incident patients at index date, per year	100
Table A5. Description of medical history and comorbidities in AF incident patients at index date, per year	105
Table A6. Description of concomitant treatments in AF incident patients at index date, per year	110
Table A7. Description of sociodemographic characteristics in AF incident patients at index date, years 2016-2019	120
Table A8. Description of medical history and comorbidities in AF incident patients at index date, years 2016-2019	125
Table A9. Description of concomitant treatments in AF incident patients at index date, years 2016-2019	130
Table A10. Risk of stroke, major bleeding or death in AF incident patients	131
Table A11. Risk of stroke, major bleeding or death in AF incident patients with a high thromboembolic risk (modified CHA2DS2VASC score is ≥ 2 for males and ≥ 3 females)	132
Table A12. Annual incidence rate of all AF patients between 2016 and 2019 (2020 for sensitivity analyses) in France	133
Table A13. Annual prevalence of all AF patients between 2016 and 2019 (2020 for sensitivity analyses) in France	134
Table A14. Description of OAC treatment pattern during the follow-up	135
Table A15. Description of HCRU and associated costs (including event related cost): <time period> ...	140
Table A16. Overall comparison of HCRU and associated cost (during all the follow-up)	149
Table A17. Number of occurrences of HCRU 6 and 12 months before and after the first stroke for patients exposed to OAC.....	150
 Figure A1. Flow chart of the selection of the study population.....	96
Figure A2. Example of sunburst to OAC treatment pattern	138
Figure A3. Example of Kaplan Meier curves of persistence rate in months	139

1. Shell Tables and Figures of Results of the Selection of the Study Population

[figure not shown]

Figure A1. Flow chart of the selection of the study population

Table A1. Description of the follow-up of the AF incident population

	Exposed to OAC (N=XXX)	Unexposed to OAC (N=XXX)	Overall (N=XXX)
Reason for censoring the follow-up: n (%)			
Death	xx.x (xx.x)	xx.x (xx.x)	xx.x (xx.x)
Lost to follow-up	xx.x (xx.x)	xx.x (xx.x)	xx.x (xx.x)
End of study period	xx.x (xx.x)	xx.x (xx.x)	xx.x (xx.x)
Duration of the follow-up in years			
Mean (std)	xx.x (xx.x)	xx.x (xx.x)	xx.x (xx.x)
Median	xx.x	xx.x	xx.x
Q1 - Q3	xx.x - xx.x	xx.x - xx.x	xx.x - xx.x
Min - Max	xx.x - xx.x	xx.x - xx.x	xx.x - xx.x
Duration group of the follow-up in years: n (%)			
[0-1[xx.x (xx.x)	xx.x (xx.x)	xx.x (xx.x)
[1-2[xx.x (xx.x)	xx.x (xx.x)	xx.x (xx.x)
[2-3[xx.x (xx.x)	xx.x (xx.x)	xx.x (xx.x)
[3-4[xx.x (xx.x)	xx.x (xx.x)	xx.x (xx.x)
[4-5]*	xx.x (xx.x)	xx.x (xx.x)	xx.x (xx.x)

*This category will be display only for the sensitivity analysis (up to 2020)

2. Shell Tables and Figures of Results of the Planned Analysis for the Primary Objective

Table A2. Incidence rate for stroke, major bleeding and death in AF incidents patients between 2016 and 2019 in France – <POPULATION>

<POPULATION>	Stroke				Major bleeding				Death			
	n	N	Crude	Standardized **	n	N	Crude	Standardized %**	n	N	Crude	Standardized **
Overall	x	x	x,x [x,x;x,x]	NA	x	x	x,x [x,x;x,x]	NA	x	x	x,x [x,x;x,x]	NA
CI 95%				NA				NA				NA
Unexposed to OAC*	x	x	x,x [x,x;x,x]	x,x [x,x;x,x]	x	x	x,x [x,x;x,x]	x,x [x,x;x,x]	x	x	x,x [x,x;x,x]	x,x [x,x;x,x]
CI 95%												
Exposed to OAC	x	x	x,x [x,x;x,x]	NA	x	x	x,x [x,x;x,x]	NA	x	x	x,x [x,x;x,x]	NA
CI 95%				NA				NA				NA
VKAs	x	x	x,x [x,x;x,x]	NA	x	x	x,x [x,x;x,x]	NA	x	x	x,x [x,x;x,x]	NA
CI 95%				NA				NA				NA
DOACs	x	x	x,x [x,x;x,x]	NA	x	x	x,x [x,x;x,x]	NA	x	x	x,x [x,x;x,x]	NA
CI 95%				NA				NA				NA
Apixaban	x	x	x,x [x,x;x,x]	NA	x	x	x,x [x,x;x,x]	NA	x	x	x,x [x,x;x,x]	NA
CI 95%				NA				NA				NA
Dabigatran	x	x	x,x [x,x;x,x]	NA	x	x	x,x [x,x;x,x]	NA	x	x	x,x [x,x;x,x]	NA
CI 95%				NA				NA				NA
Rivaroxaban	x	x	x,x [x,x;x,x]	NA	x	x	x,x [x,x;x,x]	NA	x	x	x,x [x,x;x,x]	NA
CI 95%				NA				NA				NA

OAC: Oral anticoagulant; DOACs: Direct oral anticoagulants; VKAs: Antivitamins K; NA, not applicable.

n: number of events of interest; N: number of person-years of follow-up

*Unexposed and exposed to OAC correspond to the period of time where the patients are not exposed to OAC and exposed to OAC, respectively

%: Incidence of the event of interest; CI 95%: 95% confidence interval

**: Standardized on age group (<65 years old; 65-74 years old; 75-79 years old; ≥80 years old) using the exposed population as reference

<POPULATION>: Incidence rate of events will be stratified in the following sub-groups:

Incident elderly AF patient (≥80 years old)

Incident AF patient having a history of coronary arterial disease (CAD)

Incident AF frail patient

Incident AF patient having an active cancer

Incident AF patient reported with previous stroke

Modified CHAD2DS2VASC score groups (Low risk / Moderate risk/ High

This table will be presented for sensitivity analyses:

- with integration of 2020 data;
- with a grace period of 30 days and 90 days;
- with integration of all incident AF patients (i.e. inclusion of patients with an event of interest between inclusion date and index date).

Table A3. Incidence rate for ischemic and hemorrhagic stroke in AF incidents patients between 2016 and 2019 in France

<POPULATION>	Stroke							
	Ischemic				Hemorrhagic			
	n	N	Crude	Standardized **	n	N	Crude	Standardized **
Overall	x	x	x,x	NA	x	x	x,x	NA
CI 95%			[x,x;x,x]	NA			[x,x;x,x]	NA
Unexposed to OAC*	x	x	x,x	x,x	x	x	x,x	x,x
CI 95%			[x,x;x,x]	[x,x;x,x]			[x,x;x,x]	[x,x;x,x]
Exposed to OAC*	x	x	x,x	x,x	x	x	x,x	x,x
CI 95%			[x,x;x,x]	[x,x;x,x]			[x,x;x,x]	[x,x;x,x]
VKAs	x	x	x,x	x,x	x	x	x,x	x,x
CI 95%			[x,x;x,x]	[x,x;x,x]			[x,x;x,x]	[x,x;x,x]
DOACs	x	x	x,x	x,x	x	x	x,x	x,x
CI 95%			[x,x;x,x]	[x,x;x,x]			[x,x;x,x]	[x,x;x,x]
Apixaban	x	x	x,x	x,x	x	x	x,x	x,x
CI 95%			[x,x;x,x]	[x,x;x,x]			[x,x;x,x]	[x,x;x,x]
Dabigatran	x	x	x,x	x,x	x	x	x,x	x,x
CI 95%			[x,x;x,x]	[x,x;x,x]			[x,x;x,x]	[x,x;x,x]
Rivaroxaban	x	x	x,x	x,x	x	x	x,x	x,x
CI 95%			[x,x;x,x]	[x,x;x,x]			[x,x;x,x]	[x,x;x,x]

OAC: Oral anticoagulant; DOACs: Direct oral anticoagulants; VKAs: Antivitamins K; NA, not applicable.

n: number of events of interest; N: number of person-years of follow-up

*Unexposed to OAC and exposed to OAC correspond to the period of time where the patients are not exposed to OAC and exposed to OAC respectively

** Standardized on age group (<65 years old; 65-74 years old; 75-79 years old; ≥80 years old) using the exposed population as reference.

3. Shell Tables and Figures of Results of the Planned Analysis for the Secondary Objectives

3.1. To describe the characteristics of AF incidents patients at index date, per year

Table A4. Description of sociodemographic characteristics in AF incident patients at index date, per year

	Exposed to OAC				Total exposed to OAC			Unexposed to OAC			Total unexposed To OAC	
	2016 (N=XXX)	2017 (N=XXX)	2018 (N=XXX)	2019 (N=XXX)	2016-2019 (N=XXX)	2016 (N=XXX)	2017 (N=XXX)	2018 (N=XXX)	2019 (N=XXX)	2016-2019 (N=XXX)		
	Age in years	xx.x	xx.x	xx.x	xx.x	xx.x	xx.x	xx.x (xx.x)	xx.x (xx.x)	xx.x (xx.x)		
Mean (std)	(xx.x)	(xx.x)	(xx.x)	(xx.x)	xx.x (xx.x)	(xx.x)	(xx.x)	xx.x (xx.x)	xx.x (xx.x)	xx.x (xx.x)		
Median	xx.x	xx.x	xx.x	xx.x	xx.x	xx.x	xx.x	xx.x	xx.x	xx.x		
Q1 - Q3	xx.x –	xx.x –	xx.x –	xx.x –	xx.x – xx.x	xx.x	xx.x	xx.x – xx.x	xx.x – xx.x	xx.x – xx.x		
Min - Max	xx.x	xx.x	xx.x	xx.x	xx.x – xx.x	xx.x	xx.x	xx.x – xx.x	xx.x – xx.x	xx.x – xx.x		
Age group: n (%)	xx.x	xx.x	xx.x	xx.x	xx.x (xx.x)	xx.x	xx.x	xx.x (xx.x)	xx.x (xx.x)	xx.x (xx.x)		
<80 years	(xx.x)	(xx.x)	(xx.x)	(xx.x)	(xx.x)	(xx.x)	(xx.x)	(xx.x)	(xx.x)	(xx.x)		
80-90 years	(xx.x)	(xx.x)	(xx.x)	(xx.x)	(xx.x)	(xx.x)	(xx.x)	(xx.x)	(xx.x)	(xx.x)		
>90 years	(xx.x)	(xx.x)	(xx.x)	(xx.x)	(xx.x)	(xx.x)	(xx.x)	(xx.x)	(xx.x)	(xx.x)		
Sex: n (%)	xx.x	xx.x	xx.x	xx.x	xx.x (xx.x)	xx.x	xx.x	xx.x (xx.x)	xx.x (xx.x)	xx.x (xx.x)		
Female	(xx.x)	(xx.x)	(xx.x)	(xx.x)	(xx.x)	(xx.x)	(xx.x)	(xx.x)	(xx.x)	(xx.x)		

	Exposed to OAC				Total exposed to OAC			Unexposed to OAC			Total unexposed To OAC	
	2016 (N=XXX)	2017 (N=XXX)	2018 (N=XXX)	2019 (N=XXX)	2016-2019 (N=XXX)	2016 (N=XXX)	2017 (N=XXX)	2018 (N=XXX)	2019 (N=XXX)	2016-2019 (N=XXX)	2016-2019 (N=XXX)	
	xx.x	xx.x	xx.x	xx.x	xx.x (xx.x)	xx.x	xx.x	xx.x (xx.x)	xx.x (xx.x)	xx.x (xx.x)	xx.x (xx.x)	
Male	(xx.x)	(xx.x)	(xx.x)	(xx.x)		(xx.x)	(xx.x)					
Exposed to DOACs, at index date: n (%)	xx.x	xx.x	xx.x	xx.x	xx.x (xx.x)	xx.x	xx.x	xx.x (xx.x)	xx.x (xx.x)	xx.x (xx.x)	xx.x (xx.x)	
	(xx.x)	(xx.x)	(xx.x)	(xx.x)		(xx.x)	(xx.x)					
Apixaban	xx.x	xx.x	xx.x	xx.x	xx.x (xx.x)	xx.x	xx.x	xx.x (xx.x)	xx.x (xx.x)	xx.x (xx.x)	xx.x (xx.x)	
Dabigatran	(xx.x)	(xx.x)	(xx.x)	(xx.x)		(xx.x)	(xx.x)					
	xx.x	xx.x	xx.x	xx.x	xx.x (xx.x)	xx.x	xx.x	xx.x (xx.x)	xx.x (xx.x)	xx.x (xx.x)	xx.x (xx.x)	
Rivaroxaban	(xx.x)	(xx.x)	(xx.x)	(xx.x)		(xx.x)	(xx.x)					
Exposed to VKA, at index date: n (%)	xx.x	xx.x	xx.x	xx.x	xx.x (xx.x)	xx.x	xx.x	xx.x (xx.x)	xx.x (xx.x)	xx.x (xx.x)	xx.x (xx.x)	
	(xx.x)	(xx.x)	(xx.x)	(xx.x)		(xx.x)	(xx.x)					
Contraindications to OAC, at index date: n (%)	xx.x	xx.x	xx.x	xx.x	xx.x (xx.x)	xx.x	xx.x	xx.x	xx.x (xx.x)			
	(xx.x)	(xx.x)	(xx.x)	(xx.x)		(xx.x)	(xx.x)	(xx.x)	(xx.x)			
Complimentary universal health care (CMU-c): n (%)	xx.x	xx.x	xx.x	xx.x	xx.x (xx.x)	xx.x	xx.x	xx.x (xx.x)	xx.x (xx.x)	xx.x (xx.x)	xx.x (xx.x)	
	(xx.x)	(xx.x)	(xx.x)	(xx.x)		(xx.x)	(xx.x)	(xx.x)	(xx.x)			
Yes	xx.x	xx.x	xx.x	xx.x	xx.x (xx.x)	xx.x	xx.x	xx.x (xx.x)	xx.x (xx.x)	xx.x (xx.x)	xx.x (xx.x)	
	(xx.x)	(xx.x)	(xx.x)	(xx.x)		(xx.x)	(xx.x)					

	Exposed to OAC				Total exposed to OAC			Unexposed to OAC			Total unexposed To OAC	
	2016 (N=XXX)	2017 (N=XXX)	2018 (N=XXX)	2019 (N=XXX)	2016-2019 (N=XXX)	2016 (N=XXX)	2017 (N=XXX)	2018 (N=XXX)	2019 (N=XXX)	2016-2019 (N=XXX)	2016-2019 (N=XXX)	
	xx.x	xx.x	xx.x	xx.x	xx.x (xx.x)	xx.x	xx.x	xx.x (xx.x)	xx.x (xx.x)	xx.x (xx.x)	xx.x (xx.x)	
No	(xx.x)	(xx.x)	(xx.x)	(xx.x)		(xx.x)	(xx.x)					
Aid for complementary health care (ACS) for elderly patients: n (%)												
Yes	xx.x (xx.x)	xx.x (xx.x)	xx.x (xx.x)	xx.x (xx.x)	xx.x (xx.x)	xx.x (xx.x)	xx.x (xx.x)	xx.x (xx.x)	xx.x (xx.x)	xx.x (xx.x)	xx.x (xx.x)	
No	(xx.x)	(xx.x)	(xx.x)	(xx.x)		(xx.x)	(xx.x)					
Area of residence: n (%)												
Ile de France	xx.x (xx.x)	xx.x (xx.x)	xx.x (xx.x)	xx.x (xx.x)	xx.x (xx.x)	xx.x (xx.x)	xx.x (xx.x)	xx.x (xx.x)	xx.x (xx.x)	xx.x (xx.x)	xx.x (xx.x)	
Centre-Val de Loire	xx.x (xx.x)	xx.x (xx.x)	xx.x (xx.x)	xx.x (xx.x)	xx.x (xx.x)	xx.x (xx.x)	xx.x (xx.x)	xx.x (xx.x)	xx.x (xx.x)	xx.x (xx.x)	xx.x (xx.x)	
Bourgogne-Franche-Comté	xx.x (xx.x)	xx.x (xx.x)	xx.x (xx.x)	xx.x (xx.x)	xx.x (xx.x)	xx.x (xx.x)	xx.x (xx.x)	xx.x (xx.x)	xx.x (xx.x)	xx.x (xx.x)	xx.x (xx.x)	
Normandie	xx.x (xx.x)	xx.x (xx.x)	xx.x (xx.x)	xx.x (xx.x)	xx.x (xx.x)	xx.x (xx.x)	xx.x (xx.x)	xx.x (xx.x)	xx.x (xx.x)	xx.x (xx.x)	xx.x (xx.x)	
Hauts-de-France	xx.x (xx.x)	xx.x (xx.x)	xx.x (xx.x)	xx.x (xx.x)	xx.x (xx.x)	xx.x (xx.x)	xx.x (xx.x)	xx.x (xx.x)	xx.x (xx.x)	xx.x (xx.x)	xx.x (xx.x)	

	Exposed to OAC				Total exposed to OAC			Unexposed to OAC			Total unexposed To OAC	
	2016 (N=XXX)	2017 (N=XXX)	2018 (N=XXX)	2019 (N=XXX)	2016-2019 (N=XXX)	2016 (N=XXX)	2017 (N=XXX)	2018 (N=XXX)	2019 (N=XXX)	2016-2019 (N=XXX)		
	2016 (N=XXX)	2017 (N=XXX)	2018 (N=XXX)	2019 (N=XXX)	2016-2019 (N=XXX)	2016 (N=XXX)	2017 (N=XXX)	2018 (N=XXX)	2019 (N=XXX)	2016-2019 (N=XXX)		
Grand-Est	xx.x (xx.x)	xx.x (xx.x)	xx.x (xx.x)	xx.x (xx.x)	xx.x (xx.x)	xx.x (xx.x)	xx.x (xx.x)	xx.x (xx.x)	xx.x (xx.x)	xx.x (xx.x)		
Pays de la Loire	xx.x (xx.x)	xx.x (xx.x)	xx.x (xx.x)	xx.x (xx.x)	xx.x (xx.x)	xx.x (xx.x)	xx.x (xx.x)	xx.x (xx.x)	xx.x (xx.x)	xx.x (xx.x)		
Bretagne	xx.x (xx.x)	xx.x (xx.x)	xx.x (xx.x)	xx.x (xx.x)	xx.x (xx.x)	xx.x (xx.x)	xx.x (xx.x)	xx.x (xx.x)	xx.x (xx.x)	xx.x (xx.x)		
Nouvelle Aquitaine	xx.x (xx.x)	xx.x (xx.x)	xx.x (xx.x)	xx.x (xx.x)	xx.x (xx.x)	xx.x (xx.x)	xx.x (xx.x)	xx.x (xx.x)	xx.x (xx.x)	xx.x (xx.x)		
Occitanie	xx.x (xx.x)	xx.x (xx.x)	xx.x (xx.x)	xx.x (xx.x)	xx.x (xx.x)	xx.x (xx.x)	xx.x (xx.x)	xx.x (xx.x)	xx.x (xx.x)	xx.x (xx.x)		
Auvergne-Rhône-Alpes	xx.x (xx.x)	xx.x (xx.x)	xx.x (xx.x)	xx.x (xx.x)	xx.x (xx.x)	xx.x (xx.x)	xx.x (xx.x)	xx.x (xx.x)	xx.x (xx.x)	xx.x (xx.x)		
Provence-Alpes-Côte d'Azur	xx.x (xx.x)	xx.x (xx.x)	xx.x (xx.x)	xx.x (xx.x)	xx.x (xx.x)	xx.x (xx.x)	xx.x (xx.x)	xx.x (xx.x)	xx.x (xx.x)	xx.x (xx.x)		
Corse	xx.x (xx.x)	xx.x (xx.x)	xx.x (xx.x)	xx.x (xx.x)	xx.x (xx.x)	xx.x (xx.x)	xx.x (xx.x)	xx.x (xx.x)	xx.x (xx.x)	xx.x (xx.x)		
Overseas districts and territories	xx.x (xx.x)	xx.x (xx.x)	xx.x (xx.x)	xx.x (xx.x)	xx.x (xx.x)	xx.x (xx.x)	xx.x (xx.x)	xx.x (xx.x)	xx.x (xx.x)	xx.x (xx.x)		
Frail patient: n (%)												
Yes	xx.x (xx.x)	xx.x (xx.x)	xx.x (xx.x)	xx.x (xx.x)	xx.x (xx.x)	xx.x (xx.x)	xx.x (xx.x)	xx.x (xx.x)	xx.x (xx.x)	xx.x (xx.x)		

	Exposed to OAC				Total exposed to OAC			Unexposed to OAC			Total unexposed To OAC	
	2016 (N=XXX)	2017 (N=XXX)	2018 (N=XXX)	2019 (N=XXX)	2016-2019 (N=XXX)	2016 (N=XXX)	2017 (N=XXX)	2018 (N=XXX)	2019 (N=XXX)	2016-2019 (N=XXX)		
	No	xx.x (xx.x)	xx.x (xx.x)	xx.x (xx.x)	xx.x (xx.x)	xx.x (xx.x)	xx.x (xx.x)	xx.x (xx.x)	xx.x (xx.x)	xx.x (xx.x)	xx.x (xx.x)	xx.x (xx.x)
Modified CHAD₂DS₂VASC score strata: n (%)												
Low												
(xx.x) (xx.x) (xx.x) (xx.x) xx.x (xx.x)												
Moderate												
(xx.x) (xx.x) (xx.x) (xx.x) xx.x (xx.x)												
High												
HAS-BLED score: n (%)												
Mean (std)												
(xx.x) (xx.x) (xx.x) (xx.x) xx.x (xx.x)												
Median												
xx.x – xx.x												
Q1 - Q3												
xx.x – xx.x												
Min - Max												
xx.x – xx.x												

Sociodemographic characteristics with integration of 2020 data will be presented for sensitivity analyses

Table A5. Description of medical history and comorbidities in AF incident patients at index date, per year

	Exposed to OAC				Total exposed to OAC		Unexposed to OAC				Total unexposed to OAC	
	2016 (N=XXX)	2017 (N=XXX)	2018 (N=XXX)	2019 (N=XXX)	2016-2019 (N=XXX)	2016 (N=XXX)	2017 (N=XXX)	2018 (N=XXX)	2019 (N=XXX)	2016-2019 (N=XXX)	2016-2019 (N=XXX)	
	Stroke: n (%)	xx.x	xx.x	xx.x	xx.x	xx.x (xx.x)	xx.x	xx.x (xx.x)	xx.x	xx.x	xx.x (xx.x)	
Ischemic	(xx.x)	(xx.x)	(xx.x)	(xx.x)		(xx.x)		(xx.x)	(xx.x)	(xx.x)	(xx.x)	
	xx.x	xx.x	xx.x	xx.x	xx.x (xx.x)	xx.x	xx.x (xx.x)	xx.x	xx.x	xx.x (xx.x)		
Hemorrhagic	(xx.x)	(xx.x)	(xx.x)	(xx.x)		(xx.x)		(xx.x)	(xx.x)	(xx.x)		
Comorbidities: n (%)		xx.x	xx.x	xx.x	xx.x	xx.x (xx.x)	xx.x	xx.x (xx.x)	xx.x	xx.x	xx.x (xx.x)	
CAD	(xx.x)	(xx.x)	(xx.x)	(xx.x)		(xx.x)		(xx.x)	(xx.x)	(xx.x)		
	xx.x	xx.x	xx.x	xx.x	xx.x (xx.x)	xx.x	xx.x (xx.x)	xx.x	xx.x	xx.x (xx.x)		
Dementia	(xx.x)	(xx.x)	(xx.x)	(xx.x)		(xx.x)		(xx.x)	(xx.x)	(xx.x)		
Myocardial infarction	xx.x (xx.x)	xx.x (xx.x)	xx.x (xx.x)	xx.x (xx.x)	xx.x (xx.x)	xx.x (xx.x)	xx.x	xx.x (xx.x)				
	xx.x	xx.x	xx.x	xx.x	xx.x (xx.x)	xx.x	xx.x (xx.x)	xx.x	xx.x	xx.x (xx.x)		
Congestive Heart failure	(xx.x)	(xx.x)	(xx.x)	(xx.x)		(xx.x)		(xx.x)	(xx.x)	(xx.x)		
Peripheral arterial disease	xx.x (xx.x)	xx.x (xx.x)	xx.x (xx.x)	xx.x (xx.x)		(xx.x)		(xx.x)	(xx.x)	(xx.x)		
	xx.x	xx.x	xx.x	xx.x	xx.x (xx.x)	xx.x	xx.x (xx.x)	xx.x	xx.x	xx.x (xx.x)		
Other vascular diseases	(xx.x)	(xx.x)	(xx.x)	(xx.x)		(xx.x)		(xx.x)	(xx.x)	(xx.x)		
	xx.x	xx.x	xx.x	xx.x	xx.x (xx.x)	xx.x	xx.x (xx.x)	xx.x	xx.x	xx.x (xx.x)		
Sleep disorders	(xx.x)	(xx.x)	(xx.x)	(xx.x)		(xx.x)		(xx.x)	(xx.x)	(xx.x)		

	Exposed to OAC				Total exposed to OAC	Unexposed to OAC				Total unexposed to OAC
	2016 (N=XXX)	2017 (N=XXX)	2018 (N=XXX)	2019 (N=XXX)		2016 (N=XXX)	2017 (N=XXX)	2018 (N=XXX)	2019 (N=XXX)	
	xx.x	xx.x	xx.x	xx.x	xx.x (xx.x)	xx.x	xx.x (xx.x)	xx.x	xx.x	xx.x (xx.x)
Active cancer	(xx.x)	(xx.x)	(xx.x)	(xx.x)		(xx.x)		(xx.x)	(xx.x)	
	xx.x	xx.x	xx.x	xx.x	xx.x (xx.x)	xx.x	xx.x (xx.x)	xx.x	xx.x	xx.x (xx.x)
Malnutrition	(xx.x)	(xx.x)	(xx.x)	(xx.x)		(xx.x)		(xx.x)	(xx.x)	
	xx.x	xx.x	xx.x	xx.x	xx.x (xx.x)	xx.x	xx.x (xx.x)	xx.x	xx.x	xx.x (xx.x)
Morbid Obesity	(xx.x)	(xx.x)	(xx.x)	(xx.x)		(xx.x)		(xx.x)	(xx.x)	
	xx.x	xx.x	xx.x	xx.x	xx.x (xx.x)	xx.x	xx.x (xx.x)	xx.x	xx.x	xx.x (xx.x)
Anemia	(xx.x)	(xx.x)	(xx.x)	(xx.x)		(xx.x)		(xx.x)	(xx.x)	
	xx.x	xx.x	xx.x	xx.x	xx.x (xx.x)	xx.x	xx.x (xx.x)	xx.x	xx.x	xx.x (xx.x)
COPD	(xx.x)	(xx.x)	(xx.x)	(xx.x)		(xx.x)		(xx.x)	(xx.x)	
	xx.x	xx.x	xx.x	xx.x	xx.x xx.x (xx.x)	xx.x	xx.x	xx.x	xx.x	xx.x (xx.x)
Diabetes	(xx.x)	(xx.x)	(xx.x)	(xx.x)	(xx.x)	(xx.x)	(xx.x)	(xx.x)	(xx.x)	
	xx.x	xx.x	xx.x	xx.x	xx.x xx.x (xx.x)	xx.x	xx.x	xx.x	xx.x	xx.x (xx.x)
Diabetes with complications	(xx.x)	(xx.x)	(xx.x)	(xx.x)	(xx.x)	(xx.x)	(xx.x)	(xx.x)	(xx.x)	
	xx.x	xx.x	xx.x	xx.x	xx.x xx.x (xx.x)	xx.x	xx.x	xx.x	xx.x	xx.x (xx.x)
Connective tissue disease	xx.x	xx.x	xx.x	xx.x	xx.x	xx.x xx.x (xx.x)	xx.x	xx.x	xx.x	xx.x (xx.x)
	(xx.x)	(xx.x)	(xx.x)	(xx.x)	(xx.x)	(xx.x)	(xx.x)	(xx.x)	(xx.x)	
Ulcer disease	xx.x	xx.x	xx.x	xx.x	xx.x	xx.x xx.x (xx.x)	xx.x	xx.x	xx.x	xx.x (xx.x)
